**Declarations of interest:**

None

## Statistical Analysis

Sample size calculation was performed by n4Studies with the hypothesis that lung ultrasonography is not inferior to fiberoptic bronchoscopy (non-inferiority study) 10, 18, 19. Non-inferiority margin equal 10% with significant *p*-value as 0.05, power 90%, the sample size each group equal 82 cases. Furthermore, concerning drop out about 15%, sample size of each group was 100.

Statistical analysis was performed using SPSS version 18 for Windows (Chicago, IL). Continuous variables with normal distribution were presented as means and standard deviation, non-normal variables were report as median and interquartile range. Comparison of demographic data, rate of lung collapse and duration were made with the independent t test, Mann Whitney U test or Pearson's chi-squared test. Statistical significance was represented by *p* value <0.05. The positive predictive value was calculated to determine the effectiveness of lung ultrasound compared to fiberoptic bronchoscopy.

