Instead, lung ultrasonography is a novel, safe and easy way to detect lung collapse, which has high sensitivity and specificity(5). There is also a study report 88% of accuracy of lung ultrasound in the diagnosis of anesthesia-induced atelectasis in children(8,9). The recent study also reports superior lung ultrasonography over clinical methods. Meanwhile, the misplacement of DLT in both groups could not be ensured(3). Therefore, this method might be useful for caring for thoracic patients. However, due to its new method, lung ultrasonography needs some practice and learning curve(10).

Objectives: This study aimed to demonstrate that using lung ultrasonography to confirm lung collapse resulted from proper positioning of the double lumen tube (DLT) is a comparable method to using fiberoptic bronchoscopy to confirm the DLT position.

Design: a non-inferiority randomized controlled study

Setting: A tertiary care university hospital, single institution

Participants: Two-hundreds patients with ASA classification 1-3 scheduled for elective thoracic surgery who require a left-side double lumen tube were enrolled and randomized into 2 groups. Five patients were dropped out from the protocol deviation.

Interventions:

In group FOB (n=98), standard fiberoptic bronchoscope was used to confirm the position of the DLT and adjusted the tube to proper position, while in group US (n=97), lung ultrasound was scanned in 4 zones including upper and lower lobe at flank and back of patient at the side of surgery to confirm the lung collapse resulted from proper positioning of the DLT and used to aid repositioning of the DLT if required.

Outcome Measurements: The degree of lung collapse was determined by visual grading by surgeon. Time used to adjust the DLT position was recorded.

Statistical Analysis

Sample size calculation was performed by *Mario de Bellis et al* (11) report that fiberoptic bronchoscopy provided a sensitivity of 95% for optimal LDLT position. Moreover, *Parab et al*(5) and *Chou et al*(12) report the sensitivity of lung ultrasonography to confirm lung collapse at 88-100%. As a result, we hypothesized that lung ultrasonography is not inferior to fiberoptic bronchoscopy (non-inferiority study). Non-inferiority margin equal 10% with significant *p*-value as 0.05, power 90%, the sample size each group equal 82 cases. Furthermore, concerning drop out about 15%, sample size of each group was 100. Sample size calculation was demonstrated from n4Studies as

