$$n_2 = \frac{(z_{1-\alpha} + z_{1-\beta})^2}{(\epsilon - \delta)^2} \left[\frac{p_1(1-p_1)}{k} + p_2(1-p_2) \right]$$
$$\epsilon = p_1 - p_2, \quad k = \frac{n_1}{n_2}, \quad n_1 = kn_2$$

For a non-inferiority or superiority trial for binary data

Proportion in group1 (p1) = 0.950

Proportion in group2 (p2) = 0.950

Non-inferiority or superiority margin (δ) = 0.100

Ratio between 2 groups (k) = 1.0

[figure not shown]
Alpha (α) = 0.05, Z (0.950) = 1.644854

Beta (β) = 0.10, Z (0.900) = 1.281552

Sample size: n1 = 82, n2 = 82

Statistical analysis was performed using SPSS version 18 for Windows (Chicago, USA). Continuous data were presented as the means and SD and statistical significance was considered when $p < 0.05$. The positive predictive value was calculated to determine the effectiveness of lung ultrasound compared to fiberoptic bronchoscopy and defined as follow: Positive predictive value (%) = TP/(TP+FP) x100

Figure 1: Trial profile

References

4. Cohen E. Double-lumen tube position should be confirmed by fiberoptic bronchoscopy. *Curr Opin Anaesthesiol.* 2004;17(1):1-6.
6. Lohser J. Evidence-based management of one-lung ventilation. *Anesthesiol Clin.* 2008;26(2):241-72, v.

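### In the available text, the 10-point non-inferiority margin is tied to no named outcome, and collapse rate and positive predictive value can give different answers

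*SAP*

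**What the plan says.** The protocol sets the design: "Design: a non-inferiority randomized controlled study". Its sample-size calculation compares two proportions, both 0.95, with a margin of 0.10. The error rates are "Alpha (α) = 0.05, Z (0.950) = 1.644854" and "Beta (β) = 0.10, Z (0.900) = 1.281552", so the planned test is one-sided at 5% with 90% power. The text introduces the 95% as the sensitivity of bronchoscopy for optimal tube position.

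The Outcome Measurements paragraph reads: "The degree of lung collapse was determined by visual grading by surgeon. Time used to adjust the DLT position was recorded". Neither outcome is called primary.

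The SAP's Statistical Analysis section names the comparisons: "Comparison of demographic data, rate of lung collapse and duration were made with the independent t test, Mann Whitney U test or Pearson's chi-squared test". It then sets one threshold: "Statistical significance was represented by *p* value <0.05". It repeats the margin, significance level, power and sample size, but does not link the margin to any of these comparisons.

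Both statistics sections give PPV a special role. In the protocol's words: "The positive predictive value was calculated to determine the effectiveness of lung ultrasound compared to fiberoptic bronchoscopy". The protocol defines it as TP/(TP+FP). Neither document gives it a test, an interval or a threshold.

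**The concern.** A non-inferiority conclusion needs one quantity, one margin and one decision rule. Here four different quantities sit near the conclusion: sensitivity for tube position (sample size), degree of collapse (protocol outcome), rate of collapse (SAP comparison) and PPV (effectiveness). The visible text gives no cut point by which a surgeon's grade becomes a rate.

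Two things are at stake. First, collapse rate and PPV are different quantities. The rate can be taken over all randomised patients. PPV is taken only over patients whose check was positive, so patients whom the method did not declare well placed leave its denominator. Second, the planned 5% error and 90% power describe one binary contrast. They do not describe a conclusion that could rest on whichever proportion or cut point comes out well.

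**Working it through.** **1. The plan's own figure.** Inputs from the protocol's sample-size calculation: p1 = p2 = 0.95, margin 0.10, k = 1, z = 1.644854 and 1.281552.

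n = (1.644854 + 1.281552)² / 0.10² × (0.95×0.05 + 0.95×0.05) = 81.4, so 82 per group.

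This matches the stated 82. With 15% dropout, 82/0.85 = 96.5, which the plan takes up to 100. The calculation is sound for a single binary contrast; what is missing is the name of that contrast.

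**2. Which quantity appears where.**

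| Place | Quantity | Link to the 10-point margin |
|---|---|---|
| Protocol, sample size | sensitivity for tube position, 95% | margin used; trial outcome not named |
| Protocol, Outcome Measurements | degree of collapse; adjustment time | none |
| SAP, Statistical Analysis | rate of collapse; duration | none; difference tests at p<0.05 |
| Both statistics sections | PPV | none; said to determine effectiveness |

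**3. Can collapse rate and PPV disagree?** The counts are illustrative, not trial data. Group sizes are the reported 97 (US) and 98 (FOB). Assume that PPV is computed within each arm with collapse as the reference. Suppose 88 US patients are positive on ultrasound and 85 of them collapse, while the other 9 do not. In FOB all 98 are positive and 93 collapse.

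Lower one-sided 95% bound = d − 1.644854 × √[pU(1−pU)/nU + pF(1−pF)/nF].

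- Collapse rate: 85/97 = 87.6% against 93/98 = 94.9%. d = −7.3 points, SE = 4.01, bound = −7.27 − 6.60 = −13.9. This is below −10, so non-inferiority is not shown.
- PPV: 85/88 = 96.6% against 93/98 = 94.9%. d = +1.7 points, SE = 2.95, bound = 1.69 − 4.85 = −3.2. This is above −10, so non-inferiority would be declared.

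The same patients give two answers.

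**4. Do the named tests settle it?** Take collapse in 88/97 against 93/98, again illustrative. Pearson's chi-squared test gives p = 0.26. The difference is −4.2 points with SE 3.69, so the bound is −4.18 − 6.07 = −10.2. A non-significant difference test can therefore accompany a result that fails the margin.

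**5. Error if either of two candidates may carry the claim.** Suppose each is tested at one-sided 5% and ultrasound is truly at the margin on both. The chance that at least one passes is 1 − Φ₂(1.645, 1.645; ρ):

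- ρ = 0: 1 − 0.95² = 9.75%
- ρ = 0.5: 8.8%
- ρ = 0.8: 7.5%

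The number of candidates and ρ are assumptions; the documents give neither. As ρ approaches 1 the figure returns to 5%.

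**The case against.** The strongest reply is that the documents narrow the choice. The sample-size calculation is labelled as being for binary data, so the margin can apply only to a proportion. That rules out duration and an uncut grade. The objective is to confirm lung collapse, and rate of collapse is the only outcome proportion in the SAP's list of comparisons. Degree and rate may be one outcome in two forms. Part of the SAP, before its Statistical Analysis section, was not available and may name a primary outcome or a cut point.

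Much of this stands. Rate of collapse is the natural candidate, and the absence can be asserted only for the available text. But the inference is left to the reader, and the plan's own words point elsewhere, by giving the judgement of effectiveness to PPV and basing the 95% on tube position. Even if rate is meant, no visible cut point defines it and no visible rule compares it with the margin.

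A reader might also infer that four outcomes are all tested at p<0.05, so that the false-positive risk about doubles. The documents do not support that. PPV is calculated, not tested, and degree is not in the SAP's list. The listed tests are difference tests, so their combined error is not the risk of a false non-inferiority claim. A near-doubling fits only two roughly independent candidates that are each tested against the margin.

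Another tempting reading is that different cut points would give opposite conclusions in about half of trials. That needs an assumed three-grade scale with assumed top-grade rates. Most of the disagreement is low power at the stricter cut, which is failure to show non-inferiority and not an opposite finding. In the same example, an unpooled z test already has about 6% error at the more lenient cut alone.

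**Conclusion.** The concern holds in this form: in the available text the 10-point margin is attached to no named outcome, no cut point converts grade to rate, and the only quantity said to determine effectiveness has no decision rule and can disagree with the collapse rate. The comparisons as written never test the margin.

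The -13.9 and -3.2 bounds show that disagreement is possible; they do not estimate how often it would occur. The error of about 7.5-9.8%, against a planned 5%, applies only if two proportions or cut points could each carry the conclusion, at correlations of 0.8 to 0. The sample size is not affected. The main limit on confidence is the unavailable part of the SAP. The point should be corrected, but it does not show that the trial reached a wrong conclusion.

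**What to change.** In the protocol's Outcome Measurements and the SAP's Statistical Analysis:

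- Name one primary comparison: the proportion of randomised patients with successful lung collapse, US minus FOB, with one stated cut point on the surgeon's grade.
- State the rule: non-inferiority is concluded only if the lower one-sided 95% confidence bound lies above -10 points. This matches the z of 1.644854 used in planning.
- Label the full grade distribution, PPV and duration as secondary or supportive.
- If the unavailable part of the SAP already names a primary outcome and cut point, repeat them in these two sections and tie the margin to them there.

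The protocol already reports 98 and 97 patients in the past tense, so pre-specification may no longer be possible. If the data were seen before the cut point was fixed, report the collapse result at every cut point and state that the choice was post hoc.

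The cost is wording and, in the post hoc case, a fuller results table. No extra patients are needed, and 82 per group (100 with dropout) stands. The downside is that PPV and duration can no longer support a confirmatory claim on their own.

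### The trial is sized for non-inferiority with a 10-point margin, but the available plan analyses lung collapse only with tests of difference and never compares a result with the margin

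*SAP*

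**What the plan says.** The protocol states "Design: a non-inferiority randomized controlled study". The SAP's Statistical Analysis section says the sample size was calculated "with the hypothesis that lung ultrasonography is not inferior to fiberoptic bronchoscopy (non-inferiority study"), with a 10% margin, p-value 0.05, 90% power and 82 per group, raised to 100 for dropout. The protocol's sample-size working uses 95% in both groups, a margin of 0.100 and "Z (0.950) = 1.644854". That value is the one-sided 5% normal quantile, although the words one-sided do not appear.

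The outcome is described in the protocol only as follows: "The degree of lung collapse was determined by visual grading by surgeon". No grade cut-off is given.

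For the analysis, the SAP says comparisons of demographic data, "rate of lung collapse and duration were made with the independent t test, Mann Whitney U test or" Pearson's chi-squared test, with significance at p<0.05. It adds: "The positive predictive value was calculated to determine the effectiveness of lung ultrasound compared to fiberoptic bronchoscopy". The protocol defines that quantity as TP/(TP+FP). Neither document attaches a margin, an interval or a between-arm contrast to it.

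The protocol reports 98 patients in the FOB group and 97 in the US group, and states: "Five patients were dropped out from the protocol deviation".

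**The concern.** A t test, a Mann-Whitney test and a Pearson chi-squared test all ask whether two groups differ. A non-inferiority claim needs the data to exclude a deficit as large as the margin. Failing to find a difference does not do that, and finding a small difference does not rule it out.

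In the available text the margin appears only in the sample-size calculation. With no rule tied to it, a non-significant p-value could be taken as proof that ultrasound is no worse, when the interval still includes a deficit of more than 10 points. The opposite mistake is also possible: a significant difference could be read as failure when the deficit is shown to be inside the margin. The trial's central conclusion is at stake in both cases.

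**Working it through.** **Inputs.** From the protocol: p1 = p2 = 0.95, margin 0.10, z = 1.644854 and 1.281552, ratio 1:1, group sizes 98 (FOB) and 97 (US). Assumed here: a binary lung-collapse outcome, analysed by the uncorrected Pearson chi-squared test. The SAP lists three tests without assigning them to outcomes, and chi-squared is the natural one for a rate.

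**1. The plan's own figure.** With zero true difference, n = (1.644854 + 1.281552)² × (0.95×0.05 + 0.95×0.05) / 0.10² = 8.5639 × 0.095 / 0.01 = 81.36, so 82 per group. This matches. One-sided 0.025 would give 100, so the design alpha is one-sided 0.05.

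**2. What follows if p≥0.05 is read as non-inferior.** For each pair of true rates exactly 10 points apart, sum the joint binomial probability of every outcome pair (98 FOB, 97 US) with chi-squared p≥0.05:

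| True FOB / US | P(p≥0.05) | P(90% Newcombe lower bound > -10 points) |
|---|---|---|
| 98% / 88% | 16.0% | 4.4% |
| 95% / 85% | 33.6% | 4.95% |
| 90% / 80% | 49.5% | 5.1% |
| 80% / 70% | 63.1% | 5.1% |

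The range matters because the 95% used for sizing is a sensitivity for tube position, not a lung-collapse rate. At the planned 82 per group, the 95% / 85% figure for p≥0.05 is 41.5%.

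**3. Illustrative counts.** The Newcombe lower bound is d − √[(pU − lU)² + (uF − pF)²], where d = pU − pF, lU is the lower Wilson limit for US and uF the upper Wilson limit for FOB, each at z = 1.644854.

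For FOB 93/98 and US 87/97: pF = 0.9490, uF = 0.9749, pU = 0.8969, lU = 0.8349. Then d = −0.0521 and the bound is −0.0521 − √(0.0620² + 0.0260²) = −0.119. Chi-squared p = 0.172: no significant difference, but non-inferiority is not shown.

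With FOB fixed at 93/98:

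| US | chi-squared p | 90% Newcombe lower bound |
|---|---|---|
| 85/97 | 0.072 | −14.3 points |
| 87/97 | 0.172 | −11.9 points |
| 88/97 | 0.26 | −10.7 points |
| 89/97 | 0.38 | −9.5 points |

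Every US count from 85 to 88 is non-significant yet fails the margin. The bound first clears it at 89.

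In the other direction, 98/98 against 93/97 gives Pearson p = 0.042 with a bound of −8.9 points: significantly different, yet non-inferior.

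**4. Does a margin-based rule keep the design?** At 98/97 and true rates of 95% in both arms:

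| Interval | Power | False claims at 95% / 85% |
|---|---|---|
| 90% Newcombe | 89.9% | 4.95% |
| 95% Newcombe | 81.2% | 2.3% |
| 90% Wald | 93.1% | 6.1% |
| 95% Wald | 88.4% | 3.3% |

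Power depends on the true common rate: the 90% Newcombe rule gives 98.8% at 98% and 73.4% at 90%.

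**5. Analysis set.** Assume 100 randomised per arm, so 2 FOB and 3 US patients were dropped. Then 93/98 against 89/97 passes at −9.5 points. Counting the five as failures gives 93/100 against 89/100, with a bound of −11.0, which fails.

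**The case against.** Part of the SAP was not available for review, so a decision rule there cannot be excluded. That limit stands. However, both documents' statistical sections were available, and neither contains such a rule.

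The SAP does not assign chi-squared to lung collapse, and since the surgeon grades the degree of collapse, a Mann-Whitney test on grades is possible. That is fair, and the error rates above depend on the chi-squared reading. The defect does not, because a Mann-Whitney test has no link to a 10-point margin either.

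The 16% to 63% range rests on a reading of p≥0.05 that the documents never state. That is correct: these figures measure a possible misreading and are not operating characteristics of a stated rule. The absence of any rule is not conditional.

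The reverse example is sparse, with about two expected failures per arm. Fisher's exact test gives p = 0.059, and a 95% Newcombe bound would be −10.1. It holds for the Pearson test the SAP names and a 90% interval, and the main argument does not need it.

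Newcombe is one valid method among several, and a 95% Wald interval loses less power than a 95% Newcombe interval. True; the preference rests on its false-claim rate being closest to the 5% used for sizing.

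Finally, arm-level counts would let any reader compute the interval. They would, but the choice of endpoint, interval and analysis set would then not be prespecified.

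**Conclusion.** The concern holds and must be fixed. The hypothesis, margin and sample size are for non-inferiority, while the only between-group analyses in the available text are tests of difference. Followed as written, the analysis does not test the hypothesis the trial was sized for. The positive predictive value does not fill the gap.

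If a non-significant result were taken as non-inferiority, the chance of a false claim at a true 10-point deficit would be about one in three at the plan's own 95% rate, against the planned one in twenty. This size assumes a binary outcome, the Pearson chi-squared test, 98 and 97 patients, and that reading of p≥0.05. One-sided 0.05 is inferred from the z value and from 82 per group reproducing at that level. The core finding rests on none of the size assumptions.

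**What to change.** 1. Name one binary surgeon-graded lung-collapse endpoint as primary and state the grade cut-off.
2. Make its primary analysis the risk difference, US minus FOB, with a two-sided 90% Newcombe confidence interval (matching one-sided 0.05), in place of the difference test.
3. Declare non-inferiority only if the lower bound is above −10 percentage points.
4. State the primary analysis set. Report the interval both for all randomised patients by assigned arm and for the 195 analysed, and say how the five dropped patients are handled.
5. State that p≥0.05 from a difference test is not evidence of non-inferiority, and that the positive predictive value is descriptive. Keep the difference tests for demographics and duration.

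The cost is SAP wording and one interval in two analysis sets, with no new patients. Outcomes for the five dropped patients are needed, or a stated assumption for them. The power of about 90% relies on the 98 and 97 patients obtained; the same enumeration at 82 per group gives 85.2%. The protocol already reports dropouts and group sizes in the past tense, so full prespecification may no longer be possible. If the data were seen before the change, label the analysis post hoc.
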